Table 14-2	Follow Up Requirements for Liver Events and Laboratory Triggers ...	44
Table 15-1	Specific Renal Alert Criteria and Actions.....	46

List of figures

Figure 3-1	Study design	14
------------	--------------------	----

List of abbreviations

AE	Adverse Event
Alb	albumin
ALP	Alkaline Phosphatase
ALT	Alanine Aminotransferase
AMD	aged-related macular degeneration
AST	Aspartate Aminotransferase
CAN	Canakinumab
CAPS	Cryopyrin Associated Periodic Syndrome
CFR	US Code of Federal Regulations
CRF	Case Report/Record Form (paper or electronic)
crFMF	colchicine resistant Familial Mediterranean Fever
CPO	Country Pharma Organization
CRO	Contract Research Organization
CTC	Common Toxicity Criteria
ECG	Electrocardiogram
FMF	Familial Mediterranean Fever
GCP	Good Clinical Practice
HIDS	Hyper IgD Syndrome
IB	Investigator Brochure
ICH	International Conference on Harmonization of Technical Requirements for Registration of Pharmaceuticals for Human Use
IEC	Independent Ethics Committee
IL	interleukin
i.v.	intravenous
IRB	Institutional Review Board
LFT	Liver function test
MedDRA	Medical dictionary for regulatory activities
MKD	Mevalonate Kinase Deficiency
OC/RDC	Oracle Clinical/Remote Data Capture
PGA	Physician's Global Assessment of Disease Activity
PSW	premature subject withdrawal

q4w	Every 4 weeks
q8w	Every 8 weeks
SAE	Serious Adverse Event
SJIA	systemic juvenile idiopathic arthritis
SUSAR	Suspected Unexpected Serious Adverse Reactions
TBL	Total bilirubin
TD	Study Treatment Discontinuation
TRAPS	TNF-receptor Associated Periodic Syndrome
WHO	World Health Organization

Glossary of terms

Cohort	A specific group of patients/subjects fulfilling certain criteria
Dosage	Dose of the study treatment given to the patient in a time unit (e.g. 100 mg once a day, 75 mg twice a day)
Enrollment	Point/time of patient entry into the study at which informed consent must be obtained (e.g. prior to starting any of the procedures described in the protocol)
Epoch	A portion of the study which serves a specific purpose. Typical epochs are: screening/recruitment, wash-out, treatment, and follow-up
Investigational drug	The drug whose properties are being tested in the study; this definition is consistent with US CFR 21 Section 312.3 and is synonymous with “investigational new drug” or “investigational medicinal product.”
Patient/subject ID	A unique number assigned to each patient upon signing the informed consent
Study drug/ treatment	Any single drug or combination of drugs administered to the patient as part of the required study procedures; includes investigational drug (s) or background therapy
Study Treatment Discontinuation (TD)	When the subject permanently stops taking study treatment prior to the defined study treatment completion date
Variable	A measured value or assessed response that is determined in specific assessments and used in data analysis to evaluate the drug being tested in the study
Withdrawal of consent	Withdrawal of consent from the study is defined as when a patient does not want to participate in the study any longer, and does not want any further visits or assessments, and does not want any further study related contact, and does not allow analysis of already obtained biologic material

Protocol summary

Protocol number	CACZ885N2301E2
Title	An extension study of CACZ885N2301, multi-center, open label study of canakinumab in Japanese patients with Periodic Fever Syndromes (TRAPS, HIDS, or crFMF)
Brief title	An extension study of safety of canakinumab in Japanese patients with Periodic Fever Syndromes
Sponsor and Clinical Phase	Novartis Phase III
Investigation type	Drug
Study type	Interventional
Purpose and rationale	
This is an open label extension study to 'A randomized, double-blind, placebo controlled study of canakinumab in patients with Periodic Fever Syndromes (TRAPS, HIDS, or crFMF), with subsequent randomized withdrawal/ dosing frequency reduction and open-label long term treatment epochs' (CACZ885N2301).
 
This extension study offers the opportunity for patients who completed Epoch 4 of the preceding CACZ885N2301 study to continue to be treated with ACZ885 until approval in Japan of the drug in Periodic Fever Syndromes or until development of ACZ885 in Periodic Fever Syndromes is suspended.

Primary Objective	The primary objective of this study is to evaluate safety and tolerability of ACZ885 in this extension study.
Secondary Objectives	Not applicable.
Study design	
Japanese patients are allowed to enter this extension study after completion of Epoch 4 (an open-label treatment epoch) in CACZ885N2301 study. This study consists of two study epochs (Screening epoch and Extension-treatment epoch). This study will be continued until approval in Japan or the discontinuation of the development of the drug in Periodic Fever Syndromes.
 
In this study, all patients will receive the same dose and regimen as administered at the end of study CACZ885N2301 consisting of 1 or 2 subcutaneous injections every 4 or 8 weeks. Safety will be evaluated every 8 weeks.

Population	Completed Epoch 4 of the CACZ885N2301 study in Japan before the approval of canakinumab in Japan.
Inclusion criteria	
 Completed Epoch 4 of the CACZ885N2301 study in Japan before the approval of canakinumab in Japan. Before or at Visit 1, written informed consent must be obtained before any assessment is performed from those ≥ 20 years of age. Parent or legal guardian's written informed consent and child's assent, if appropriate, are required before any assessment is performed for patients < 20 years of age.

Exclusion criteria	
 • Any conditions or significant medical problems in which the investigator judges the patient should not enter this extension study. • Pregnant or nursing (lactating) women • Female adolescents (\leq 18 years of age) of childbearing potential who do not agree to abstinence or, if sexually active, do not agree to the use of contraception. • Women of child-bearing potential, defined as all women physiologically capable of becoming pregnant, unless they are using effective methods of contraception during dosing of study treatment.
Investigational and reference therapy	
 • Canakinumab solution for injection in vial which contains 150 mg canakinumab in 1 mL solution
Efficacy assessments	
 • Not applicable.
Safety assessments	
 • Physical examination • Laboratory evaluations • Pregnancy and assessments of fertility
Other assessments	
 • No additional tests will be performed.
Data analysis	
Due to a very limited number of patients enrolled, specific listings will be produced for reporting purpose, and no statistical analysis will be performed.
 
Primary variable is adverse events.
 
Adverse events will be coded using the MedDRA dictionary that provides the primary system organ class and preferred term information.
 
A listing will be presented to display individual adverse events reported

Key words	
Canakinumab, interleukin-1, Periodic Fevers Syndrome, TRAPS, HIDS, crFMF, auto-inflammatory diseases, extension study

1 Introduction

1.1 Background

Periodic Fever Syndromes, also referred to as Hereditary Recurrent Fevers or Monogenic Autoinflammatory Disorders, is a group of rare orphan diseases classified together under a single term and classically consists of 4 separate conditions: Cryopyrin Associated Periodic Syndrome (CAPS), TNF receptor Associated Periodic Syndrome (TRAPS), Hyper IgD Syndrome (HIDS)/ Mevalonate Kinase Deficiency (MKD) and Familial Mediterranean Fever (FMF) ([Drenth and van der Meer 2001](#), [Goldbach-Mansky 2012](#), [Stojanov and Kastner 2005](#), [Touitou and Koné-Paut 2008](#)). There are currently no approved treatments for TRAPS, HIDS/MKD and colchicine resistant FMF (crFMF).

A key feature of these conditions is the recurrent episodes of systemic inflammation with high and disabling fever that is accompanied by characteristic signs and symptoms of target organs and body systems (i.e. serositis, neutrophilic rash, muco-cutaneous ulcers, arthralgia/arthritis, and aseptic meningitis/headaches) ([Ter Haar et al 2013](#), [Piram et al 2011](#)).

The grouping of these conditions is also based on their pathophysiology, since they are now recognized as part of the expanding group of autoinflammatory disorders, which can be distinguished from autoimmune disorders by the absence of autoantibodies or antigen-specific T cells. Instead of a pathophysiology based on an adaptive immune response involving antibodies and lymphocytes, the disease mechanisms in these conditions involve innate immune regulation of cytokines and neutrophilic inflammation ([Hoffman and Simon 2009](#)).

Genome-wide association studies have begun to elucidate the molecular basis of complex autoinflammatory diseases. The discovery of disease-causing genetic variants has defined autoinflammation as a disorder within the innate immune system, implicating IL-1 as a key cytokine, and has led to a breakthrough in therapy, with IL-1 inhibitors producing rapid and sustained amelioration of symptoms ([Aksentijevich and Kastner 2011](#)).

Canakinumab (ACZ885) is a high-affinity fully human monoclonal anti-human interleukin-1 β (IL-1 β) antibody of the IgG1/ κ isotype. Canakinumab is designed to bind to human IL-1 β blocking the interaction of this cytokine to its receptors, thus functionally neutralizing the bioactivity of this cytokine, IL-1 β is recognized as one of the principal pro inflammatory cytokines in a variety of inflammatory conditions ([Dinarello et al 2012](#)).

As of 30th June 2015, approximately 10,510 patients (578 of pediatric age) received ILARIS treatment in Novartis-sponsored investigational clinical trials in a wide spectrum of IL-1 β driven diseases such as: CAPS, mild asthma, psoriasis, wet aged-related macular degeneration (AMD), gouty arthritis, type 2 diabetes mellitus, rheumatoid arthritis, and systemic juvenile idiopathic arthritis (SJIA). The post-marketing cumulative patient exposure since the first launch of the product is estimated to be approximately 6,922.7 patient-treatment-years (Investigator Brochure Edition 14.0).

Canakinumab has already been shown to be effective in treating pediatric and adult patients with 2 inherited auto-inflammatory conditions, in studies of CAPS ([Lachmann et al 2009](#), [Kuemmerle-Deschner et al 2011a](#), [Kuemmerle-Deschner et al 2011b](#), [Koné-Paut et al 2011](#)) and in more recent studies of SJIA ([Ruperto et al 2012](#)). Both of these conditions consist of a spectrum of inherited defects and clinical syndromes, which all respond to canakinumab. In

addition, canakinumab has been shown to be effective in isolated case reports and preliminary studies of Periodic Fever Syndromes ([Gattorno et al 2012](#), [Gul et al 2012](#)).

In over 70 countries, canakinumab has been approved in the indications of either CAPS and/ or SJIA for which inflammation and related symptoms are expected to be caused by over-production of IL-1 β .

In CAPS, canakinumab (starting dose of 150 mg s.c. or 2 mg/kg every 8 weeks with the option to raise the dose up to a maximum of 600 mg or 8 mg/kg) produced a rapid and complete resolution of signs and symptoms in almost all patients, with an immediate and sustained normalization of all serological and hematological markers of inflammation. Signs and symptoms started to normalize within 1 day and more than 70% of the patients achieved a complete clinical response within 2 to 8 days, which was sustained. Response was independent of age, gender, and disease phenotype.

Over the last few years there has been an increasing body of literature about the efficacy of targeting IL-1 in a wide spectrum of auto-inflammatory conditions. In addition to isolated case reports of the efficacy of canakinumab in auto-inflammatory disorders, a preliminary demonstration of the efficacy and safety of canakinumab for the treatment of TRAPS, HIDS/MKD and crFMF has been provided by the results of 4 proof of concept (PoC), open label studies in patients with TRAPS (20 adult and pediatric patients), HIDS (9 adult and pediatric patients), and colchicine resistant/intolerant FMF (one study in 9 adults and one study in 7 pediatric patients).

In all 4 PoC studies, using various dosing regimens, results of the primary endpoint showed rates of responses $\geq 85\%$ in each of the 3 conditions with clinically meaningful improvements observed across a spectrum of measures (physician and patient based) and in inflammatory biomarkers. In addition, no new safety signals emerged in the study population.

These preliminary encouraging results warranted the further assessment of the benefit/risk of canakinumab treatment in a Phase III program in patients suffering from these 3 rare conditions. Results from the primary N2301 study Epoch 2 have formed the basis of global regulatory filing for the treatment of the studied indications with canakinumab. This extension study is planned to offer the opportunity to continue the treatment with ACZ885 until approval in Japan or the discontinuation of the development of the drug in Periodic Fever Syndromes. Eligible patients are those in Japan who completed Epoch 4 of CACZ885N2301 study.

1.2 Purpose

This is an open label extension study to ‘A randomized, double-blind, placebo controlled study of canakinumab in patients with Periodic Fever Syndromes (TRAPS, HIDS, or crFMF), with subsequent randomized withdrawal/ dosing frequency reduction and open-label long term treatment epochs’ (CACZ885N2301). The primary objective of the preceding CACZ885N2301 study was to demonstrate that subcutaneous canakinumab administered every 4 weeks is superior to placebo in achieving a clinically meaningful reduction of disease activity defined as resolution of the index flare at Day 15 and no new disease flares over 16 weeks of treatment.

This extension study offers the opportunity for patients who completed Epoch 4 of the preceding CACZ885N2301 study to continue to be treated with ACZ885 until approval in Japan of the

drug in Periodic Fever Syndromes or until development of ACZ885 in Periodic Fever Syndromes is suspended.

2 Study objectives and endpoints

2.1 Primary objective

The primary objective of this study is to evaluate safety and tolerability of ACZ885 in this extension study.

2.2 Secondary objective(s)

Not applicable.

2.3 Exploratory objectives

Not applicable.

3 Investigational plan

3.1 Study design

Japanese patients are allowed to enter this extension study after completion of Epoch 4 (an open-label treatment epoch) in CACZ885N2301 study. This study consists of two study epochs (Screening epoch and Extension-treatment epoch). This study will be continued until approval in Japan or the discontinuation of the development of the drug in Periodic Fever Syndromes.

In this study, all patients will receive the same dose and regimen as administered at the end of study CACZ885N2301 consisting of 1 or 2 subcutaneous injections every 4 or 8 weeks. Safety will be evaluated every 8 weeks.

3.1.1 Screening epoch (Epoch 1)

At Visit 1, patients will be assessed for eligibility ([Section 4](#)) for study participation after completion of Epoch 4 of the CACZ885N2301 study.

Visit 1 of this extension study and Visit 399 of the CACZ885N2301 study are conducted on the same day.

3.1.2 Extension-treatment epoch (Epoch 2)

Patients who meet entry criteria at Visit 1 will enter the extension-treatment epoch (epoch 2). Since eligible patients initiate the extension-treatment epoch on the same day of screening, their first two visits (Visit 1 and Visit 101) can be on the same day.

Patients will continue the study drug based on the final dose and regimen administered at the end of the CACZ885N2301 study. All patients will receive 1 or 2 ACZ885 subcutaneous injections every 4 or 8 weeks. Stepwise up-titration up to a dosing regimen of ACZ885 300 mg (or 4 mg/kg for patients weighing ≤ 40 kg) every 4 weeks (q4w) will be allowed. In case of re-

[figure not shown]
flare [Physician’s global assessment of disease activity (PGA) ≥ 2 AND CRP ≥ 30 mg/L], patients will be allowed to increase the dose as follows and accordingly to the same up-titration scheme in study CACZ885N2301: If flare occurs at the last visit (V399) or visit between V309 and V399 of CACZ885N2301 study, up-titration will be allowed at visit 101.

- If patients receive ACZ885 150 mg (or 2 mg/kg for patients weighing ≤ 40 kg) every 8 weeks (q8w), they will increase the dose to ACZ885 150 mg q4w.
- If patients receive ACZ885 150 mg (or 2 mg/kg for patients weighing ≤ 40 kg) q4w, they will increase the dose to ACZ885 300 mg q4w.
- If patients receive ACZ885 300 mg (or 4 mg/kg for patients weighing ≤ 40 kg) q8w, they will increase the dose to ACZ885 300 mg q4w.

If flare occurs at the last visit (V399) it will be recorded in the CACZ885N2301 study. Safety will be evaluated every 8 weeks in the extension- treatment epoch (epoch 2). Patients receiving ACZ885 q4w or up-titrated to q4w administration, will come back every 4 weeks for unscheduled visits in addition to the scheduled visits as indicated in [Table 6-1](#)

For all patients, a safety follow-up visit should be conducted (e.g. by telephone) 30 days after study treatment discontinuation (TD)/ premature subject withdrawal (PSW), or 8 weeks after last injection of investigational drug, whichever is later ([Table 6-1](#)).

Figure 3-1 Study design

All patients will receive the same dose and regimen as administered at the end of study CACZ885N2301.

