5.2 Treatment arms

Patients will continue the study drug based on final dose regimen received (e.g. one of the following regimen) in the CACZ885N2301 study.

- ACZ885 150 mg (or 2 mg/kg for patients weighing ≤ 40 kg) q4w
- ACZ885 150 mg (or 2 mg/kg for patients weighing ≤ 40 kg) q8w
- ACZ885 300 mg (or 4 mg/kg for patients weighing ≤ 40 kg) q4w
- ACZ885 300 mg (or 4 mg/kg for patients weighing ≤ 40 kg) q8w

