5.5.5 Permitted dose adjustments and interruptions of study treatment

Investigational treatment dose adjustments and/or interruptions other than those detailed in [Section 3.1.2](#) are not permitted.

All dose changes must be recorded on the Dosage Administration Record CRF.

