S = assessment to be recorded on source documentation only

*These assessments are also to be conducted for patients who discontinue

Visit 1 of this extension study and Visit 399 of the CACZ885N2301 study are conducted on the same day. Visit 1 and Visit 101 can be on the same day

1. Patients receiving ACZ885 q4w or up-titrated to q4w administration will come back every 4 weeks for unscheduled visits at Day 813, Day 869 and so forth in addition to the scheduled visits

2. These assessments are source documentation only and will not be entered into the CRF, because they will be used only for dose adjustment or judgement of up-titration due to flare. Flare is defined as simultaneous occurrence of a clinical flare and a serological flare defined as follows:

- PGA \geq 2 (clinical flare)

- CRP \geq 30 mg/L (serological flare)

3. Body weight to the nearest 0.1 kilogram (kg) in indoor clothing, but without shoes

4. The PGA (physician's global assessment) will be based on a 5-point scale:

- 0 = None (no) disease associated clinical signs and symptoms

- 1 = Minimal disease associated signs and symptoms

- 2 = Mild disease associated signs and symptoms

- 3 = Moderate disease associated signs and symptoms

- 4 = Severe disease associated signs and symptoms

5. CRP will be measured at the local laboratory, including any unscheduled visits. CRP value will be standardized to a normal range of 0-10 mg/L.

6. After canakinumab is approved for Periodic Fever Syndromes (TRAPS, HIDS, or crFMF) in Japan, all subjects who continue study treatment at the timing will be expected to perform V199 evaluation approximately 8 weeks after their most recent assessment visit, and then will enter the safety follow-up period.

7. If V 101 of this extension study and V 399 of the CACZ885N2301 study are conducted on the same day, Physical exam, PGA, CRP, weight, local tolerability will be assessed only one time.

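### The up-titration steps in protocol Section 3.1.2 give no mg/kg target for patients of 40 kg or less, so the flat 300 mg target conflicts with the 4 mg/kg ceiling in the same section

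*Protocol*

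**What the plan says.** Protocol Section 3.1.2 allows dose increases after a re-flare (PGA of 2 or more together with CRP of 30 mg/L or more) and sets the upper limit first: "Stepwise up-titration up to a dosing regimen of ACZ885 300 mg (or 4 mg/kg for patients weighing ≤ 40 kg) every 4 weeks". Three bullets then give the steps. Each states the starting regimen with its mg/kg alternative for patients of 40 kg or less, and each states the target as a flat dose only:

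- Bullet 1, from 150 mg or 2 mg/kg: "every 8 weeks (q8w), they will increase the dose to ACZ885 150 mg q4w".
- Bullet 2, from 150 mg: "or 2 mg/kg for patients weighing ≤ 40 kg) q4w, they will increase the dose to ACZ885 300 mg q4w".
- Bullet 3, from 300 mg: "or 4 mg/kg for patients weighing ≤ 40 kg) q8w, they will increase the dose to ACZ885 300 mg q4w".

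The section adds that the increases follow the up-titration scheme of the core study, CACZ885N2301. That scheme is not reproduced in either document.

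Section 5.2 lists four regimens, all with a mg/kg alternative. The highest is "ACZ885 300 mg (or 4 mg/kg for patients weighing ≤ 40 kg) q4w". Section 5.5.5 disallows "Investigational treatment dose adjustments and/or interruptions other than those detailed in" Section 3.1.2, and Section 5.5.4 also refers to 3.1.2 for up-titration. SAP Section 1.1.2 carries the same ceiling and the same three bullets.

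**The concern.** For a patient of 40 kg or less, the ceiling and the bullets of one section give different doses. The bullets are worded as instructions, and Section 5.5.5 points to no other authority. A site that follows bullet 2 or 3 to the letter breaks the limit stated a few lines above it.

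Children are within scope. Section 4.1 sets no lower limit on age or weight, Section 6.5.3.3 provides for girls under 12, and Appendix 1 has separate laboratory criteria for patients under 18. What is at stake is a dosing error in a small child, not a statistical result.

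An error of this kind would also be hard to see in the data. Under Table 6-1, footnote 2, weight stays in the source documents because, with PGA and CRP, "they will be used only for dose adjustment or judgement of up-titration due to flare". The dose goes into the CRF but the weight does not, so an excess in mg/kg would not show in the study database.

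**Working it through.** **Inputs.** From protocol Section 3.1.2: the ceiling for patients of 40 kg or less, 4 mg/kg q4w; the flat targets, 150 mg q4w (bullet 1) and 300 mg q4w (bullets 2 and 3); the starting regimens, 2 mg/kg q8w, 2 mg/kg q4w and 4 mg/kg q8w. Neither document gives patient weights, so the weight w is assumed to be 20, 30 or 40 kg.

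**Step 1: target against ceiling.** The ceiling dose is 4w mg.

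- Bullets 2 and 3: 300/(4w) = 75/w. This is above 1 for every w below 75 kg, hence at every weight up to 40 kg.
- Bullet 1: 150/(4w) = 37.5/w. This is above 1 only below 37.5 kg.

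**Step 2: bullet 1 against its matching regimen.** Section 5.2 pairs 150 mg with 2 mg/kg. The ratio is 150/(2w) = 75/w, again above 1 at every weight up to 40 kg.

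**Step 3: size of the step, as dose per 4 weeks.** For patients above 40 kg each step doubles it: 75 to 150 mg, 150 to 300 mg, and 150 to 300 mg. For patients of 40 kg or less, read literally:

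- Bullet 1: 150/(2w/2) = 150/w
- Bullet 2: 300/(2w) = 150/w
- Bullet 3: 300/(4w/2) = 150/w

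| Weight (assumed) | Ceiling, 4 mg/kg | 300 mg in mg/kg | 300 mg / ceiling | 150 mg / ceiling | 150 mg / (2 mg/kg dose) | Step in dose per 4 weeks |
|---|---|---|---|---|---|---|
| 40 kg | 160 mg | 7.5 | 1.88 | 0.94 | 1.88 | 3.75-fold |
| 30 kg | 120 mg | 10 | 2.5 | 1.25 | 2.5 | 5-fold |
| 20 kg | 80 mg | 15 | 3.75 | 1.88 | 3.75 | 7.5-fold |

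For patients above 40 kg, bullets 1 and 3 change only the interval. Read literally for lighter patients, they raise the dose per injection as well.

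**Step 4: weight-based targets instead.** With 2 mg/kg as the target in bullet 1 and 4 mg/kg in bullets 2 and 3, the steps are 2w/w = 2, 4w/(2w) = 2 and 4w/(2w) = 2. This is the same doubling as in heavier patients, and every target is at or below the ceiling.

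**For reference.** The highest mg/kg dose mentioned anywhere in the protocol is the CAPS maximum in Section 1.1, "with the option to raise the dose up to a maximum of 600 mg or 8 mg/kg". Since 300/8 = 37.5, a flat 300 mg exceeds 8 mg/kg below 37.5 kg. That figure belongs to another indication and is not a limit in this study.

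**The case against.** The best defense is that the text has one coherent reading. The ceiling governs the bullets, Section 5.5.5 refers to 3.1.2 as a whole including the ceiling, and the only regimen in Section 5.2 that fits a step to the top dose for a small patient is 4 mg/kg q4w. For bullet 1, Section 5.2 pairs 150 mg with 2 mg/kg at both intervals. This probably is what was meant. It shows the intention without repairing the instruction: the parenthesis appears in the ceiling, in all three starting regimens and in all four regimens of Section 5.2, and is missing only from the targets.

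The core-study scheme and the Pharmacist Manual (Section 5.5.4) may also give sites the correct weight-based targets. Neither is available here, so that possibility stays open. Patients come directly from the core study, study staff give every injection (Section 6.3), sponsor medical staff can advise (Section 5.5), and dose changes and treatment errors are recorded (Sections 5.5.5 and 7.5). These safeguards lower the chance of a literal misreading. However, a dose that matches a bullet as written may not be recognized as an error.

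The excess also needs several things at once: a patient of 40 kg or less among at most 10, a qualifying flare, a regimen below the maximum, and staff who follow the bullet over the ceiling. That stands. The ratios above show what the literal text would produce and are not an expected effect. It also stands that the SAP section is a design recap that governs no dosing, and that the study produces listings only.

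**Conclusion.** The inconsistency is real and lies in an operative dosing instruction. For patients of 40 kg or less, bullets 2 and 3 exceed the section's own ceiling at every weight, by a factor of 1.88 at 40 kg rising to 3.75 at 20 kg. Bullet 1 exceeds the ceiling only below 37.5 kg but always exceeds the matching 2 mg/kg dose. The multiples rest on assumed weights; that bullets 2 and 3 break the ceiling at every weight up to 40 kg does not.

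It is most likely a drafting omission, and nothing suggests that flat dosing of small children was intended or occurred. Section 9.8 limits the study to 10 patients, and whether any weighs 40 kg or less is not stated. Because the possible error is an overdose of a child and the correction is not contentious, it should be corrected despite the small numbers.

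**What to change.** First have the sponsor confirm the up-titration scheme of the core study. Then, in protocol Section 3.1.2, add the low-weight alternative to each target in the form that Section 5.2 uses: 2 mg/kg for patients of 40 kg or less in bullet 1, and 4 mg/kg for them in bullets 2 and 3. Make the same edit in SAP Section 1.1.2 so that the documents agree.

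The text change is one parenthesis in each of three bullets, in each document. For the protocol it needs a written amendment under Section 11.1, with sponsor and IRB/IEC approval and health authority approval where required. Design, visits, data collection and planned listings do not change.
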